Protocol Title: Evaluating the addition of obturator nerve block to adductor canal block for total knee arthroplasty

PI: [name]

NCT03326999

Date: Sept 29, 2017

Protocol Title: Evaluating the addition of obturator nerve block to adductor canal block for total knee arthroplasty

Research Question: Does the addition of obturator nerve block to a regional anesthesia technique with adductor canal block and local infiltration analgesia for total knee replacement surgery reduce opioid consumption in the PACU?

Primary objective: Compare the rate of IV opioid consumption in patients who receive a combination of adductor canal block, obturator nerve block, and local infiltration analgesia at the surgical site versus patients who receive adductor canal block and local infiltration analgesia.

Secondary objectives:

- a. Measure the severity of pain at rest using an 11-point Likert scale at 1, 6, 12, 24 hour marks postoperatively in patients who receive adductor canal block, obturator nerve block, and local infiltration analgesia versus patients who receive adductor canal block and local infiltration analgesia
- b. Compare time to breakthrough pain after surgery in patients who receive adductor canal block, obturator nerve block, and local infiltration analgesia versus patients who receive adductor canal block and local infiltration
- c. Measure rate of post-operative nausea/vomiting in patients who receive adductor canal block, obturator nerve block, and local infiltration analgesia versus patients who receive adductor canal block and local infiltration
- d. Measure time to ambulation in patients who receive adductor canal block, obturator nerve block, and local infiltration analgesia versus patients who receive adductor canal block and local infiltration
- e. Compare analgesia satisfaction score at time of first postoperative followup visit in patients who receive adductor canal block, obturator nerve block, and local infiltration analgesia versus patients who receive adductor canal block and local infiltration.

## Background

The management of postoperative pain after total knee arthroplasties remains a challenging issue. Even though postoperative pain typically ranges from moderate to severe, patients are encouraged and expected to start physical therapy and ambulate as soon as possible because early rehabilitation may lead to improved long-term functional status of the knee. Integrated multimodal analgesic strategies have been employed for postoperative pain management; the aim of such strategies is to utilize different mechanisms of action to provide superior analgesia while limiting side effects and adverse events. Multimodal analgesic strategies for total knee arthroplasties most commonly combine regional anesthesia techniques, including femoral nerve block and local infiltration analgesia, with a combination of low-dose opioids, acetaminophen, and nonsteroidal anti-inflammatory drugs.

The optimal peripheral nerve block or combination of blocks is not yet known. Since the knee joint is innervated by an anterior and posterior group of sensory nerves, an approach that provides regional anesthesia to both groups seem reasonable. The femoral nerve block provides analgesia of the knee in the anteromedial region. However, despite the improved analgesia and shortened hospital stays provided by the use of femoral nerve blocks in total knee arthroplasties, the motor weakness that can be caused by these regional blocks can delay mobilization and increase the risk of falls.

Recently, the adductor canal block has become more frequently used because of claims that femoral nerve block can increase fall risk. The adductor canal block blocks the saphenous nerve and is primarily a sensory block, even though it can result in the partial motor block of the vastus medialis muscle. Overall, the adductor canal block has exhibited relative spring of quadriceps strength and was shown to be not inferior in providing analgesia and opioid consumption.

The obturator nerve block has also been utilized for total knee arthroplasties. The obturator nerve provides innervation to the posterior group of sensory nerves. The femoral nerve block has not been shown to provide consistent block of the obturator nerve, and the addition of sciatic nerve block to a femoral nerve block does not further improve analgesia of the posterior knee. However, the addition of the obturator nerve block to a femoral nerve block has been shown to improve postoperative analgesia after total knee arthroplasty. The addition of obturator nerve block to femoral triangle block has also been shown to reduce opioid consumption without impairing ambulation.

Based on the above studies, various multimodal analgesic strategies, including various combinations of regional anesthetic techniques, have been utilized, with varying success. There is no consensus on the optimal strategy that provides the most effective postoperative analgesia while preserving ambulation and limiting side effects such as nausea and vomiting. We believe that the obturator nerve block in addition to adductor canal block and local infiltration analgesia can target both the anterior and posterior distribution of nerves to the knee to provide superior analgesia while not limiting ambulation. To date, we are not aware of any studies that have examined this particular combination of regional anesthetic techniques.

#### Primary and Secondary Study Endpoints

Primary objective: Compare the rate of IV opioid consumption in patients who receive a combination of adductor canal block, obturator nerve block, and local infiltration analgesia at the surgical site versus patients who receive adductor canal block and local infiltration analgesia.

#### Secondary objectives:

- f. Measure the severity of pain at rest using an 11-point Likert scale at 1, 6, 12, 24 hour marks postoperatively in patients who receive adductor canal block, obturator nerve block, and local infiltration analgesia versus patients who receive adductor canal block and local infiltration analgesia
- g. Compare time to breakthrough pain after surgery in patients who receive adductor canal block, obturator nerve block, and local infiltration analgesia versus patients who receive adductor canal block and local infiltration

- h. Measure rate of post-operative nausea/vomiting in patients who receive adductor canal block, obturator nerve block, and local infiltration analgesia versus patients who receive adductor canal block and local infiltration
- i. Measure time to ambulation in patients who receive adductor canal block, obturator nerve block, and local infiltration analgesia versus patients who receive adductor canal block and local infiltration
- j. Compare analgesia satisfaction score at time of first postoperative follow-up visit in patients who receive adductor canal block, obturator nerve block, and local infiltration analgesia versus patients who receive adductor canal block and local infiltration.

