The study treatment you get will be chosen by chance, like flipping a coin. Neither you nor the study doctor will choose what study treatment you get. You will have an equal chance of being given each

study treatment. Neither you nor the study doctor will know which study treatment you are getting. This information could be obtained in an emergency, however.

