#### Description of instruments created by research team

The data collection sheet created by the research team will be used to gather preoperative, intraoperative, and postoperative data relevant to the study. Preoperative data to be collected includes patient demographics including age and gender. Intraoperative data include duration of surgery, total narcotics administered during surgery, and total fluids administered. Postoperative data include total narcotics administered, pain scores at regular various intervals, incidence of postoperative nausea and vomiting, and time to ambulation. Data will also be extracted from the patient's first completed physical therapy session, including total distance ambulated, pain at time of assessment, and functional mobility impairment percentage. Post-discharge data to be collected include total dosage of narcotics used after discharge, pain score, and any complications.

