Protocol Title: Evaluating the addition of obturator nerve block to adductor canal block for total knee arthroplasty

Statistical Analysis Plan

PI: [name]

NCT03326999

Date: Sept 29, 2017

Prior to the beginning of the study, a sample size calculation was performed and was based on an  $\alpha$  of 0.05 and a  $\beta$  of 0.2. Patients were randomized into an intervention and control group. Baseline characteristics of subjects in each group were compared using chi-square tests for categorical variables and independent t-tests for continuous variables. No significant differences were detected between the baseline characteristics of each group; thus, direct comparisons of the outcomes of each group were analyzed. For categorical variables, chi-square tests were utilized, unless one value in the 2x2 matrix was under 5, in which case Fischer's exact test was utilized. For binary tests, odds ratios with 95% confidence intervals were reported. For continuous variables, independent t-test was used. All calculations were performed via SAS Statistical Software (Cary, NC).

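### Does naming only a t-test for continuous outcomes leave resting pain at the four hour marks without a usable answer?

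*Protocol*

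**What the plan says.** The Protocol states the pain objective twice, as item a in the opening list and as item f under Secondary objectives: "Measure the severity of pain at rest using an 11-point Likert scale at 1, 6, 12, 24 hour marks postoperatively", comparing the arm with the added obturator block against the arm without it. The four marks stand together and none is ranked above the others. The section on instruments created by the research team describes the data sheet more loosely, as collecting "pain scores at regular various intervals".

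The SAP is one paragraph. On outcomes in general it says that "direct comparisons of the outcomes of each group were analyzed". For categorical variables it names chi-square or Fisher's exact test and adds: "For binary tests, odds ratios with 95% confidence intervals were reported". For continuous variables the whole provision is: "For continuous variables, independent t-test was used". It does not name the pain score, a key time point, a summary over time, or a rule for reading the four results together.

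**The concern.** The two sentences on outcome types are uneven. Binary outcomes get an effect size and an interval; continuous outcomes get a test. Read literally, an objective about how severe pain is could be answered by up to four p-values, which show neither how many points separate the arms nor how that changes over 24 hours.

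Four verdicts on one objective can also disagree by chance, and the SAP does not say whether they are descriptive or which one counts. At stake would be a bare non-significant result concealing a worthwhile difference, or one significant mark out of four being presented as the answer.

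Timing adds to the unease. The SAP is in the past tense and already reports a baseline result ("No significant differences were detected between the baseline characteristics of each group"), so a reader may doubt that any reading rule was fixed in advance.

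**Working it through.** **Inputs.** From the documents: four marks (Protocol, Secondary objectives); α = 0.05, stated for the sample size calculation with no sidedness given, so two-sided is assumed; equal allocation (Protocol, Description of the Study Design: "You will have an equal chance of being given each"). Patients per arm, standard deviation (SD) of the score, correlation between marks and power per mark are not in the text available, so all four are assumptions below. There is no figure in the plan to reproduce.

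**1. What the planned test already contains.** The t statistic is t = d / SE, with d the difference in means and SE = SD × √(2/n) for n per arm. The 95% interval is d ± t(0.975, 2n−2) × SE. Both parts are in hand once the test has been run.

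**2. How wide the interval would be.** Half-width = t(0.975, 2n−2) × √(2/n) × SD.
- n = 20: 2.024 × 0.316 = 0.64 SD, or 1.28 to 1.92 points for SD 2 to 3.
- n = 50: 1.984 × 0.200 = 0.40 SD, or 0.79 to 1.19 points.
- n = 100: 1.972 × 0.141 = 0.28 SD, or 0.56 to 0.84 points.

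After a non-significant result |d| is below the half-width, so the interval can reach almost twice it (up to 2 × 1.92 = 3.84 points at n = 20, SD 3). A bare non-significant result would therefore be uninformative, if that were all that was reported.

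**3. How often four verdicts would disagree.** Take the same true effect at every mark, normal test statistics with a common correlation ρ, and non-centrality 1.96 + z(power). The chance that one to three of the four marks are significant is:

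| Power per mark | ρ = 0.3 | ρ = 0.5 | ρ = 0.7 | ρ = 0.9 |
|---|---|---|---|---|
| 50% | 72% | 60% | 46% | 26% |
| 80% | 49% | 41% | 32% | 18% |

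Over power from 20% to 90% the range is 11% to 72%.

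**4. False positives with no true effect.** If the marks were independent, 1 − 0.95⁴ = 0.185. With common correlation 0.3, 0.5, 0.7 and 0.9, the chance of at least one significant mark is 17.4%, 15.6%, 13.0% and 9.4%. This misleads only if a single mark is taken as the answer.

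**5. Would writing intervals into the SAP change steps 3 and 4?** No. The 95% interval excludes zero exactly when the two-sided 5% t-test is significant, so four unadjusted intervals cross zero in the same mixed pattern. Only a rule about reading the marks together would bear on that.

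**6. Does the constant-effect model fit this design?** Doubtfully. The procedures section describes spinal anesthesia and an obturator injection of bupivacaine or saline, and mentions no catheter. The effect may well differ between 1 and 24 hours; differing verdicts could then reflect the time course, and the rates in step 3 would not apply.

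**The case for a change.** The best argument for a change is the contrast inside the SAP. Its authors wrote down an estimate and interval for one type of outcome and not for the other. A t-test makes the difference computable without committing anyone to report it, and one sentence would close the gap at almost no cost. The asymmetry is real, and a general sentence promising mean differences with 95% intervals for continuous outcomes would make the document tidier.

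That shows a line was not written; it does not show that the plan is wrong. The SAP names tests, and its silence on reporting is not a decision to publish p-values alone. The gap is also not particular to pain: the same sentence governs every continuous outcome, including IV opioid consumption if that is analysed as an amount.

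On how to read four marks together, a key time point, one analysis across time, or a descriptive label would each be acceptable. Choosing among them is a preference.

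Two side arguments carry little weight. The loose wording about the data sheet summarises a form and does not contradict the four marks in the objectives. Treating the 11-point score as categorical is remote, since the SAP discusses categorical data in terms of a 2x2 table.

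**Conclusion.** No change to the plan is needed. Followed as written, the SAP gives a valid comparison of mean resting pain at each of the four marks, and each test yields the difference and standard error from which an interval follows directly. No statement in the documents lets one significant mark decide the objective, so the false-positive rates of 9.4% to 18.5% describe a misuse that is not planned.

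The 11% to 72% range for mixed verdicts is arithmetically sound, but it rests wholly on assumed power and correlation and on a constant effect that this design may not produce. It is not evidence of harm here. Adding intervals would alter no test result and would not remove the disagreement.

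What remains is unwritten reporting detail for a secondary outcome, which analysts ordinarily fill by tabulating the four differences with their intervals. The conclusion assumes that the score is treated as continuous and that nothing in the protocol text unavailable for this check promotes a single mark.

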#### Description of Procedures Being Performed

Subjects who consent to and are scheduled for total knee arthroplasty under regional anesthesia will be invited to participate in the study during a routine preoperative visit prior to surgery. The details of the study will be reviewed and written informed consent will be obtained.

The patient will be randomized into the study group or the placebo group. On the day of surgery, the group allocation will be revealed to an anesthesiologist not part of the research study, who will receive specific instructions to prepare an injectate solution for the obturator nerve block, which will consist of 0.25% bupivacaine for the study group or saline for the placebo group.

The patient will receive midazolam for anxiolysis at the discretion of the attending anesthesiologist. An adductor canal block with 10mL 0.25% bupivacaine will be performed. An obturator nerve block will be performed with the previously prepared injectate solution. Patients will undergo spinal anesthesia with a 3mL solution of 0.75% bupivacaine. Sedation may be administered during surgery at the discretion of the anesthesiologist.

Total knee arthroplasty will be performed by the orthopedic surgeon with insertion of bicompartmental or tricompartmental prostheses using a standard medial parapatellar approach and hand-mixed cementing techniques. A local intraarticular injection will be performed intraoperatively by the surgeon, as is routinely done for total knee arthroplasties by the surgeon involved in our study, regardless of research involvement.

In the Post Anesthesia Care Unit, the patient will be administered hydromorphone using intravenous patient-controlled analgesia (PCA). Fentanyl will be administered if hydromorphone is not tolerated. Additional oral oxycodone consumption will also be recorded.

Relevant preoperative, intraoperative, and postoperative data will be obtained from the anesthesia record, the EPIC electronic medical record. The patient will also be interviewed by study personnel at time of first post-discharge follow-up visit to obtain analgesia satisfaction scores.

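### Time to ambulation is compared without allowing for the scheduled surgery slot, a cheap and possibly large loss of precision that causes no bias

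*Protocol*

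**What the plan says.** Time to ambulation is a secondary objective, item d on the protocol's first page and item i under Primary and Secondary Study Endpoints: "Measure time to ambulation in patients who receive adductor canal block, obturator nerve block, and local infiltration analgesia", compared with patients given the adductor canal block and infiltration alone. The Background hopes that the added block will improve analgesia without holding back walking. This is the only listed objective that bears on that hope.

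The SAP does not name the endpoint, so it falls under the general rule: "For continuous variables, independent t-test was used". No covariate or stratum is mentioned. After reporting that baseline tests showed no significant differences, the SAP continues: "thus, direct comparisons of the outcomes of each group were analyzed".

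On the data sheet, "Intraoperative data include duration of surgery, total narcotics administered during surgery, and total fluids administered". Duration is there, but no clock time. The source for such a field is already in use: "Relevant preoperative, intraoperative, and postoperative data will be obtained from the anesthesia record, the EPIC electronic medical record".

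**The concern.** Suppose first walking often waits for a therapist or for daytime staff. A patient whose operation ends in the morning may then walk the same day, while one whose operation ends late waits until the next morning, whichever injectate was given. Times would fall into two clusters many hours apart. An unadjusted t-test treats the distance between the clusters as random error, although part of it could be predicted from the scheduled slot, which is fixed before treatment.

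The SAP's reason for not adjusting does not meet this. A prognostic factor that is perfectly balanced between arms still inflates the error variance when it is left out. An imbalance in slot could not be seen either, because slot is not listed for collection.

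What is at stake is the width of the interval on a tolerability question. A wide interval and a non-significant test could be taken as reassurance about walking.

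**Working it through.** **Inputs from the documents.** Alpha is 0.05, and beta is 0.2, so 80% power. Allocation is equal: "You will have an equal chance of being given each" treatment. The SAP says "Prior to the beginning of the study, a sample size calculation was performed", but gives no sample size, difference or SD, so there is no figure of the plan to reproduce. Everything below rests on assumed inputs and a two-sided test.

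**Step 1: idealised shift.** Every late case walks g hours later than an early case. A share p of cases is late, and the SD within a slot is 4 h. Leaving slot out multiplies the variance by

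VIF = 1 + p(1 − p)g²/4²,

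and the 95% interval widens by √VIF. With 39 per arm and a 2.6 h difference, power is 80% when slot is accounted for. With p = 0.5:

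| Gap g | VIF | Interval wider by | Unadjusted power |
|---|---|---|---|
| 4 h | 1 + 0.25 × 16/16 = 1.25 | 12% | 71% |
| 8 h | 1 + 0.25 × 64/16 = 2.00 | 41% | 51% |
| 12 h | 1 + 0.25 × 144/16 = 3.25 | 80% | 34% |

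With p = 0.3, unadjusted power is 72%, 54% and 38%. With no gap nothing is lost. Because the delay is the same for every late case, a slot term removes all of it by construction. This step shows the mechanism, not the gain to expect.

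**Step 2: a walking window.** More realistically, a patient becomes ready some hours after surgery ends, and walks then if the clock is between 08:00 and 17:00, otherwise after 08:00 the next morning. Patients in one slot can then split between same-day and next-day walking. Assumptions: 40 per arm, a true delay of 2 h, a random wait of up to 1 h, slot split at surgery end before or after 13:00, and 1,500 simulated trials per setting (Monte Carlo error about √(0.5 × 0.5/1500) = 1.3 points). Power, t-test versus slot-adjusted:

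| Readiness, mean/SD | Two lists (ends 9–11 or 15–17) | Ends spread over 9–18 |
|---|---|---|
| 3 h/1.5 h | 36% vs 91% (+55) | 77% vs 93% (+16) |
| 4 h/1.5 h | 54% vs 89% (+35) | 79% vs 88% (+9) |
| 4 h/2 h | 56% vs 74% (+18) | 70% vs 77% (+7) |
| 5 h/2.5 h | 53% vs 59% (+6) | 56% vs 58% (+2) |

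With the window kept, 39 per arm and a readiness SD of 4 h, or with morning-only lists, the gain is 0 to 2 points. Across the settings tried, adjustment cost at most about 1 point of power.

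**Step 3: type I error.** With no true effect, the unadjusted t-test rejected in 4.3% to 5.6% of simulated trials and the slot-adjusted test in 4.3% to 5.1%.

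**Step 4: direction.** With readiness at 5 h/2.5 h, a true 2 h delay appears on average as 5.4 to 5.5 h when surgery ends at 09:00–12:00, about 3.0 h at 09:00–18:00, and 1.2 to 1.3 h at 13:00–18:00. A window can enlarge the apparent difference as well as shrink it.

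**The case against.** The strongest reply is that the mechanism is not in the documents. No section gives therapy hours, says that first walking needs a therapist, or says that cases run into the afternoon. The data sheet lists time to ambulation among the general postoperative items. Distance, pain and mobility impairment are what it takes from the first therapy session. This stands. A reader might infer that the protocol ties first walking to therapy sessions, but it does not say so.

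A second reply is that adjustment may recover little. With readiness at 5 h/2.5 h and 25 per arm, a linear term for surgery end time moved power only from 65% to 65%, 38% to 40% and 18% to 18% for morning, mixed and afternoon surgery. This stands for slow or variable recovery. It does not carry over to faster, more uniform recovery, as the upper rows in Step 2 show.

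Third, allocation is random and blinded, so the plain comparison is valid, and the primary opioid comparison is untouched. This also stands, and it makes the point one of efficiency.

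Fourth, the endpoint has no stated time origin, event definition or censoring rule. That is a separate and more basic gap. A stratum does not repair it, but can be added to whatever definition and test are adopted.

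**Conclusion.** The point holds as a low-cost improvement to a secondary analysis. The SAP's unadjusted test and the missing clock time are facts of the documents. The influence of slot on first walking is an assumption. Under an assumed 08:00–17:00 window and a 2 h delay, the gain from adjustment runs from about 0 to about 55 points of power, and the documents cannot say where in that range this trial lies.

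Three stronger readings are not supported. A reader might infer that the comparison is biased or prone to false positives, but random allocation balances slot in expectation and simulated type I error stays near 5%. A reader might infer that adjustment restores full power, but that follows only when every late case is delayed equally. A reader might infer that scheduling must hide a motor effect, but it can also magnify one.

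Whichever applies, a non-significant difference on this endpoint should not be read as evidence that the block does not limit ambulation.

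**What to change.** Add three fields to the data sheet: scheduled start of surgery, and the actual start and end clock times from the anesthesia record. In the SAP, pre-specify scheduled start, for example before or after noon, as a stratum or covariate in the time-to-ambulation comparison, and report the adjusted difference with its 95% interval. Use the scheduled start because it is fixed before treatment. Surgery end time falls after the block and should not define the stratum. The simulations split on end time, and with separate morning and afternoon lists that run to plan the two splits sort patients alike. State in the SAP that non-significance on this endpoint will not be interpreted as no effect on walking.

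The cost is a few data fields and one degree of freedom, with at most about 1 point of power lost if slot turns out not to matter.
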